#### 9.9.9. Additional Objectives

The following additional analyses will be conducted:

- Quality of Life (QOL) measures (EQ5D and SF36).
- Antihypertensive medication usage through 36 months.
- Additional procedural characteristics e.g. treatment duration, frequency of distal renal artery treatment, ablations per vessel, location of ablations, number of ablations per patient and other characteristics will be analyzed to assess their impact on blood pressure.
- Medication adherence will be assessed using results from drug testing. In addition, we will perform analyses to evaluate the effect of medication adherence on blood pressure change.
- Analyses looking at long term imaging will be performed.

RDN vs. control groups will be compared out to 6-months post randomization, prior to the crossover procedure. Statistical comparisons will be performed using the independent samples t-test for continuous endpoints and Fisher's exact test for categorical endpoints. In addition, two-sided 95% confidence intervals of the difference between RDN and control groups will be presented.

RDN vs. Crossover vs. Non-Crossover groups will be compared out to 36 months post-procedure for the RDN and Non-Crossover groups and out to 24 months for the Crossover group using chi-square tests for categorical data and ANOVA for continuous data.

Changes in blood pressure measurements from baseline to follow-up within each group will be assessed using paired t-tests. Two-sided 95% confidence intervals of the mean change from baseline will also be presented for each group.

These additional analyses will be presented for the ITT study population defined in section 9.1.3.1.

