## F.4 Two Week Screening Visit

The purpose of this visit is to assess the subject's office blood pressure two weeks after the antihypertensive medication washout period has been started. Drug-naïve patients do not need this visit. The target date is 2 weeks from the Screening 1 visit  $\pm 3$  days.

- a. **Office Blood Pressure** measurements will be obtained in accordance with Appendix L.7. This blood pressure measurement will not be used as the baseline BP measurement but will be used, in conjunction with the subject's medical history, to determine if, in the investigator's judgment, the subject's BP at Screening Visit 2 will qualify for inclusion in the study following the antihypertensive drug washout period. If the systolic OBP  $\geq 180$  mmHg, the subject must be exited from the trial. A subject who is drug naïve but still has a two week screening visit conducted, should be considered a screen failure if their office diastolic blood pressure is  $< 90$  mmHg when the subject is drug naïve at SV1 through the 2 week screening visit.
- b. **Clinical Assessment** will be conducted to further evaluate for prior or existing medical conditions that would exclude subjects from participation in the study and to establish the subject's baseline medical condition. An individual experienced in performing histories and physical exams is required to assess subjects for safety assessment during the period of time that study subjects are not on antihypertensive medications.
- c. **Medication & Adverse Event Reviews** will be completed to document baseline medication use and adverse events that occur after enrollment.

## F.5 Screening Visit 2

Screening Visit 2 must occur within 3-4 weeks of completion of SV1. The following assessments will be performed at Screening Visit 2:

- a. **EQ-5D:** The EuroQol (EQ-5D) instrument will be administered to measure baseline health outcomes.
- b. **SF-36:** The 36-Item Short Form Survey (SF-36) instrument will be administered to measure baseline health outcomes.
- c. **Clinical Assessment** will be conducted to further evaluate for prior or existing medical conditions that would exclude subjects from participation in the study and to establish the subject's baseline medical condition. An individual experienced in performing histories and physical exams is required to assess subjects for safety assessment during the period of time that study subjects are not on antihypertensive medications.

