## H.7 Additional Objectives

The following additional analyses will be conducted:

- Quality of Life (QOL) measures (EQ5D and SF36)
- Antihypertensive medication usage through 36 months.
- Additional procedural characteristics e.g. treatment duration, frequency of distal renal artery treatment, ablations per vessel, location of ablations, number of ablations per patient and other characteristics will be analyzed to assess their impact on blood pressure.
- In accordance with FDA guidance document "FDA Guidance on Conduct of Clinical Trials of Medical Products during COVID-19 Pandemic" [8], we will provide AE and SAE tables summarizing the site-reported adverse events attributed to COVID-19.

Descriptive statistics will be presented by treatment arm. Statistical comparisons between treatment arms will be made using t-tests for continuous outcomes and Fisher's exact test for categorical outcomes.

These additional analyses will be presented for the ITT study population defined in section G1.

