#### 9.9.2. Secondary Safety Objectives

The following secondary safety endpoints will be assessed:

 Acute/Procedural Safety Secondary Endpoints – Compared Between Groups at 1 Month Post-Procedure:

- Significant embolic event resulting in end-organ damage
- Renal artery perforation requiring intervention
- Renal artery dissection requiring intervention
- Vascular complications
- End-Stage Renal Disease
- ≥40% decline in eGFR
- New myocardial infarction
- New stroke
- Renal artery re-intervention
- Major bleeding according to TIMI definition (i.e. intracranial hemorrhage, ≥5g/dl decrease in hemoglobin concentration, a ≥15% absolute decrease in hematocrit, or death due to bleeding within 7 days of the procedure)
- Increase in serum creatinine >50% from Screening Visit 2
- New renal artery stenosis >70%, confirmed by angiography and as determined by the angiographic core laboratory
- Hospitalization for hypertensive crisis not related to confirmed non-adherence with medications or the protocol
- Chronic Safety Secondary Endpoints Compared Between Groups at 3, 6, 12, 24, and 36 Months Post- Randomization:
  - Composite Safety Endpoint, defined as a composite of the following events:
    - All-cause mortality
    - End-Stage Renal Disease (ESRD)
    - Significant embolic event resulting in end-organ damage
    - Renal artery perforation requiring intervention
    - Renal artery dissection requiring intervention
    - Vascular complications
    - Hospitalization for hypertensive crisis not related to confirmed non-adherence with medications and/or the protocol
    - New renal artery stenosis >70%, confirmed by angiography and as determined by the angiographic core laboratory
  - ≥ 40% decline in eGFR
  - Increase in serum creatinine >50% from Screening Visit 2
  - New myocardial infarction
  - New stroke
  - Renal artery re-intervention
  - Major bleeding according to TIMI definition (i.e. intracranial hemorrhage, ≥5g/dl decrease in hemoglobin concentration, a ≥15% absolute decrease in hematocrit, or death due to bleeding within 7 days of the procedure)
  - Hospitalization for hypertensive crisis not related to confirmed non-adherence with medication and/or protocol.
  - Summary of health related Quality of Life (HRQoL) analysis based on reporting measures using accepted QoL instruments (EQ5D and SF36).

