#### 9.9.8. Other Secondary Efficacy Endpoints

The following additional secondary efficacy endpoints will be assessed:

- Change in systolic blood pressure (SBP) from baseline (Screening Visit 2) as measured by 24-hour Ambulatory Blood Pressure Monitoring (ABPM) at 3, 6, 12, 24 and 36 months post-procedure.
- Change in office systolic blood pressure from baseline (Screening Visit 2) at 1, 3, 6, 12, 24 and 36 months post-procedure.
- Incidence of achieving target office systolic blood pressure (SBP <140 mmHg) at 1, 3, 6, 12, 24 and 36 months post-procedure.
- Change in office diastolic blood pressure from baseline (Screening Visit 2) at 1, 3, 6, 12, 24 and 36 months post-procedure.
- Change in diastolic blood pressure from baseline (Screening Visit 2) as measured by 24-hour Ambulatory Blood Pressure Monitoring (ABPM) at 3, 6, 12, 24 and 36 months post-procedure.

RDN vs. control groups will be compared out to 6-months post randomization, prior to the crossover procedure. Statistical comparisons will be performed using the independent samples t-test for continuous endpoints and Fisher's exact test for categorical endpoints. In addition, two-sided 95% confidence intervals of the difference between RDN and control groups will be presented. Changes in blood pressure measurements from baseline to follow-up within each treatment group will be assessed using paired t-tests. Two-sided 95% confidence intervals of the mean change from baseline will be presented for each treatment group. Analysis of Covariance (ANCOVA) models, adjusting the treatment effect for the baseline BP measurements will also be applied to all continuous secondary endpoints.

RDN vs. Crossover vs. Non-Crossover groups will be compared out to 36 months post-procedure for the RDN and Non-Crossover groups and out to 24 months for the Crossover group using chi-square tests for categorical data and ANOVA for continuous data.

Changes in blood pressure measurements from baseline to follow-up within each group will be assessed using paired *t*-tests. Two-sided 95% confidence intervals of the mean change from baseline will also be presented for each group.

The secondary efficacy analyses will be presented for all the study populations defined in section 9.1.3.

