#### 9.9.10. Medication Burden Analyses

Upon completion of a valid ABPM at the 3 month follow-up visit, subjects with an office SBP  $\geq$  140 mmHg will begin an antihypertensive medication regimen following protocol guidelines at the discretion of the study investigator. We will calculate the medication burden for each subject at 6, 12, 24 and 36-months using medication index scores that take into account the class, dose and frequency of each antihypertensive medication being taken.

- These scores will be compared between RDN and Control arms at the 6-month follow-up visit.
- At 12, 24 and 36 month follow-up visits, the scores will be compared between RDN, crossover and non-crossover arms.
- Multivariable predictors of medication index scores adjusting for treatment arm and BP measures will be performed.

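### EQ-5D and SF-36 are compared at 3 and 6 months by a t-test with no baseline-score covariate, although both are collected at Screening Visit 2; ANCOVA on that score would be more efficient

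*SAP*

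**What the plan says.** **Collection.** Protocol F.5 (Screening Visit 2) states: "The EuroQol (EQ-5D) instrument will be administered to measure baseline health outcomes". SF-36 is introduced there in the same terms. Protocol F.7 repeats both at 3, 6, 12, 24 and 36 months.

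**Analysis to 6 months.** SAP 9.9.9 covers the two questionnaires and compares RDN with control up to 6 months: "Statistical comparisons will be performed using the independent samples t-test for continuous endpoints". It adds a 95% confidence interval for the difference. Protocol H.7 agrees: "Statistical comparisons between treatment arms will be made using t-tests for continuous outcomes and Fisher's exact test for categorical outcomes". Neither place names a covariate or says which score is tested. The only change-from-baseline sentence in 9.9.9 concerns blood pressure.

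**ANCOVA elsewhere.** SAP 9.9.8 promises ANCOVA models "adjusting the treatment effect for the baseline BP measurements will also be applied to all continuous secondary endpoints". That section's endpoint list contains only blood pressure items. Quality of life does appear in the SAP 5.2 secondary list, so the reach of the sentence is unclear.

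**A second location.** SAP 9.9.2 places the same questionnaires at the end of the chronic safety list: "Summary of health related Quality of Life (HRQoL) analysis based on reporting measures using accepted QoL instruments (EQ5D and SF36". The text that follows says that all safety endpoints are adjudicated by the Clinical Events Committee and compares the secondary safety endpoints to 6 months by Fisher's exact test. It provides ANOVA for continuous data only after 6 months.

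**The concern.** A subject's quality-of-life score before treatment usually predicts the later score. The trial collects it and, as written, need not use it. The 3- and 6-month comparisons are the only randomized RDN-versus-control comparisons of quality of life before crossover begins. A wider interval than necessary there cannot be recovered later, and without the baseline term a chance imbalance at Screening Visit 2 passes into a follow-up-score comparison.

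The SAP already accepts the principle for blood pressure: the primary and the powered secondary endpoints are both baseline-adjusted by ANCOVA. No reason is given for treating the questionnaires differently.

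Separately, two sections assign two different tests to the same scores, and one of those tests does not suit a continuous score.

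**Working it through.** **Inputs from the documents.** Two-sided 5% level (SAP 9.2); 1:1 allocation (SAP 7); 210 to 300 subjects with 3-month data (SAP 8), hence 105 to 150 per arm. As a check on those counts, 300/0.85 = 352.9 and 210/0.85 = 247.1, which match the stated 353 and 247. They are counts for the blood pressure endpoints and serve here only as illustration.

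**Inputs the documents do not give.** There is no effect, SD, correlation or power for EQ-5D or SF-36, so there is no stated figure to reproduce. The correlation ρ between the Screening Visit 2 score and the follow-up score is assumed to be 0.3 to 0.7.

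**Variance per subject**, with the score SD set to 1 at both visits:

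- follow-up score: 1
- change score: 2(1 − ρ)
- ANCOVA on the baseline score: 1 − ρ²

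So ANCOVA has (1 − ρ²) times the variance of a follow-up-score t-test, and (1 − ρ²)/[2(1 − ρ)] = (1 + ρ)/2 times that of a change-score t-test. Both factors are below 1 for any ρ between 0 and 1.

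**Power by normal approximation.** Take the effect at which ANCOVA has 80% power, so its standardized effect is 1.960 + 0.842 = 2.802. The t-test then has power Φ(2.802·√(1 − ρ²) − 1.960) on the follow-up score and Φ(2.802·√((1 + ρ)/2) − 1.960) on the change. For ρ = 0.3 the first is Φ(2.802 × 0.954 − 1.960) = Φ(0.71) = 76%.

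| ρ | t-test, follow-up score | ANCOVA gain | t-test, change score | ANCOVA gain |
|---|---|---|---|---|
| 0.3 | 76% | 4 | 62% | 18 |
| 0.5 | 68% | 12 | 68% | 12 |
| 0.6 | 61% | 19 | 71% | 9 |
| 0.7 | 52% | 28 | 73% | 7 |

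**Other starting points.** If the t-test itself has 80% power, the gain is 3.6 to 17.5 points (follow-up score) or 13.5 down to 6.0 points (change score) over the same range of ρ. If it has 90%, the gain is 2.5 to 9.5 or 8.0 down to 4.0 points.

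**Fixed effects**, follow-up-score t-test against ANCOVA at ρ = 0.5:

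- 150 per arm, 0.3 SD: 73.8% against 85.1% (+11.3 points)
- 150 per arm, 0.5 SD: 99.1% against 99.9% (+0.8 points)
- 105 per arm, 0.3 SD: 58.5% against 70.9% (+12.4 points)
- 105 per arm, 0.5 SD: 95.2% against 98.7% (+3.5 points)

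**Interval width.** Relative to the follow-up-score t-test, the ANCOVA interval is √(1 − ρ²) as wide: 0.95 at ρ = 0.3, 0.87 at 0.5, 0.71 at 0.7. Relative to the change-score t-test it is √((1 + ρ)/2) as wide: 0.81, 0.87 and 0.92.

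**The case against.** **The endpoints are unpowered.** Both documents describe quality of life as a summary or an additional analysis, with no hypothesis or success rule. The t-test is valid under randomization, and 9.9.9 already promises a confidence interval. All of that stands, and it keeps the point small.

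**The baseline may already be used.** The SAP does not say which score is tested, and a t-test on the change uses the Screening Visit 2 value. This also stands: the defect is an unnamed score and no covariate, not a proven failure to use baseline. ANCOVA is still more precise than the change score, as the second half of the table shows.

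**A reader might infer a loss of about 12 points of power.** The documents do not support any single figure. Twelve is what ρ = 0.5 gives at one assumed effect, and ρ, effect and SD are all absent. Nor should power be worked out on the 166 and 165 subjects that Protocol B.1.2 reports as randomized. That total includes the first 80 subjects and allows for no missing scores.

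**The Fisher conflict is editorial.** The Fisher sentence follows an algorithm for adjudicated event rates, and SAP 9.2 and 9.9.9 both assign the t-test to continuous outcomes. A Fisher test on SF-36 scores is unlikely in practice. The two sections still disagree on paper.

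**A reader might extend the argument to the medication index in SAP 9.9.10.** The index needs class, dose and frequency. Protocol F.2 says only that baseline medication use is documented at Screening Visit 1, so a baseline index may not be computable. The documents do not support that change.

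**Blinding at 6 months is not fully settled.** Protocol C.5 unblinds after the 6-month tests are complete, while G.3.4 says during that visit. The order relative to the questionnaires is not stated. This does not affect the choice between t-test and ANCOVA.

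**Conclusion.** The point holds as a matter of efficiency and clarity, not validity. SAP 9.9.9 and Protocol H.7 specify a t-test for EQ-5D and SF-36 without a baseline-score covariate and without naming the analyzed score. The 9.9.8 ANCOVA does not fill the gap: even if it reaches quality of life, its covariate is baseline blood pressure.

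For an assumed ρ of 0.3 to 0.7, at an effect giving ANCOVA 80% power, the gain is about 4 to 28 points against a follow-up-score t-test, or 18 down to 7 points against a change-score t-test. It falls to under 1 point for a 0.5 SD effect with 150 per arm at ρ = 0.5. These figures rest on the normal approximation, equal SDs at the two visits and an assumed correlation; none is a property of this plan. The Fisher's exact conflict in 9.9.2 depends on no assumption but is minor.

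**What to change.** 1. In SAP 9.9.9, analyze EQ-5D and SF-36 at 3 and 6 months by ANCOVA with the Screening Visit 2 value of the same score as covariate. Report the adjusted difference and its 95% confidence interval. Keep the t-test as a supporting analysis and state which score it uses.
2. Record this in SAP 9.13 and the version history as a dated change. Protocol B.1.2 reports that the 3-month efficacy results were presented in March 2020, so the 3-month ANCOVA must be labeled as specified after that date. The opening of Protocol section H already requires departures to be described and justified in the final report.
3. Remove the quality-of-life bullet from the SAP 9.9.2 safety list, or exempt it from the Fisher's exact sentence, so that one method applies.

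Cost: SAP wording and a small amount of programming, with no new data collection. SF-36 was added in protocol version 6.0, so subjects without a Screening Visit 2 SF-36 would appear only in the unadjusted summary; their number should be reported by arm. The 3-month result also carries the label of a later change.

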#### 9.9.10. Medication Burden Analyses

Upon completion of a valid ABPM at the 3 month follow-up visit, subjects with an office SBP  $\geq$  140 mmHg will begin an antihypertensive medication regimen following protocol guidelines at the discretion of the study investigator. We will calculate the medication burden for each subject at 6, 12, 24 and 36-months using medication index scores that take into account the class, dose and frequency of each antihypertensive medication being taken.

- These scores will be compared between RDN and Control arms at the 6-month follow-up visit.
- At 12, 24 and 36 month follow-up visits, the scores will be compared between RDN, crossover and non-crossover arms.
- Multivariable predictors of medication index scores adjusting for treatment arm and BP measures will be performed.

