## **F STUDY METHODS**

### **F.1 Point of enrollment**

Patients will be pre-screened for potential enrollment in the clinical study based on prior medical history and records of office SBP. A pre-screening log will be maintained to determine the number of patients that do not meet study eligibility criteria and who will not be approached for participation in the study.

A subject is considered enrolled in this clinical study at the time at which the subject and investigator or authorized designee have personally signed and dated the Patient Information and Informed Consent Form. Written consent must have been obtained prior to Screening Visit 1 (SV1).

Investigational sites will maintain a subject identification log. However, this document will not be submitted to the sponsor.

A schedule outlining protocol required visits and assessments for subjects enrolled in the study is displayed in Table 4. A flowchart depicting the study design overview is provided in

Figure 12. The following procedures will be followed for all subjects, excluding crossovers, enrolled in this study until study exit.

[figure not shown]

Figure 12: Study Design Overview

## F.2 Screening Visit 1

After confirmation that the investigator or authorized designee and subject have personally signed and dated Patient Information and Informed Consent Form, the following assessments will be performed at Screening Visit 1:

- a) **Medical History** will be documented from the study subject to evaluate for prior or existing medical conditions and/or procedures that would exclude subjects from participation in the study.
- b) **Office Blood Pressure** measurements will be obtained in accordance with Appendix L.7. This blood pressure measurement will not be used as the baseline BP measurement but will be used, in conjunction with the subject's medical history, to determine if, in the investigator's judgment, the subject's BP at Screening Visit 2 will qualify for inclusion in the study following the antihypertensive drug washout period. However, if the subject's SBP is  $\geq 180$  mmHg, the subject will be excluded at Screening Visit 1.
- c) **Medication & Adverse Event Reviews** will be completed to document baseline medication use and adverse events that occur after enrollment.

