# 9.2. General Methodology

Descriptive statistics of continuous outcomes will be presented by treatment group and include sample size, mean, median, standard deviation, minimum and maximum. For categorical outcomes, the number and percentage of subjects in each category will be presented by treatment group. Statistical

comparisons between treatment groups will be made using the independent samples t-test for continuous outcomes and Fisher's exact test for categorical outcomes. Paired tests will be used to compare changes from baseline to follow-up within each treatment group. All statistical analyses will be performed using SAS for Windows (version 9.2 or higher) or other widely accepted statistical or graphical software. Patient data listings and tabular and graphical presentations of results will be provided. Unless otherwise specified, a two-sided 0.05 level of significance will be used to declare treatment groups significantly different.

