#### 9.7. Treatment Characteristics

Renal denervation treatment measures such as number of ablation attempts and number of generator codes will be summarized separately for each kidney, and for combined kidneys. Anti-hypertensive medication use will also be summarized at baseline and at each follow-up.

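### The 6-month medication-index comparison between arms uses no baseline covariate and so gives up precision that data already collected could supply

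*SAP*

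**What the plan says.** SAP 9.9.10 defines when the index is scored: "We will calculate the medication burden for each subject at 6, 12, 24 and 36-months using medication index scores". The pre-washout regimen is not among those time points.

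The randomized comparison is the first bullet: "These scores will be compared between RDN and Control arms at the 6-month follow-up visit". It names neither a test nor a covariate. The general rule in SAP 9.2 then governs: "comparisons between treatment groups will be made using the independent samples t-test for continuous outcomes". SAP 9.9.9 gives the same kind of test, with confidence intervals, for antihypertensive medication usage out to 6 months. The baseline-adjusted ANCOVA in SAP 9.9.8 is written for the secondary blood pressure endpoints listed there, not for the medication index.

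The third bullet of 9.9.10 is a separate model: "Multivariable predictors of medication index scores adjusting for treatment arm and BP measures will be performed". It states no visit, and it does not choose between office and 24-hour pressure. The opening of the same section gives the treatment trigger at 3 months, an office SBP at or above this level: "140 mmHg will begin an antihypertensive medication regimen following protocol guidelines at the discretion of the study investigator".

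On what is recorded before treatment, Protocol F.2 says that at SV1 a medication review "will be completed to document baseline medication use and adverse events that occur after enrollment". SAP 9.7 adds a descriptive summary: "Anti-hypertensive medication use will also be summarized at baseline and at each follow-up". Neither passage makes earlier medication a covariate.

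**The concern.** A patient's regimen before washout and off-drug pressure at SV2 should both say something about how much medication that patient needs at 6 months. Leaving them out of the comparison leaves explainable variation in the error term.

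The 6-month visit matters because it is the last one at which medication burden can be compared between arms as randomized. Control subjects may cross over after it, and 9.9.10 then compares denervation, crossover and non-crossover groups, which are no longer formed by randomization.

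The third bullet raises a different issue. Three-month office SBP is measured after randomization, is itself the powered secondary efficacy endpoint, and decides who starts drugs. If it enters the model, part of any denervation effect on medication is conditioned away. A report could then show a clear unadjusted difference beside a much smaller adjusted one, with no stated rule for reading the two.

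**Working it through.** SAP 9.9.10 gives no sample size, effect or power for the index, so there is no planned figure to reproduce. The two checks below rest on stated assumptions.

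**1. Precision from baseline covariates**

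Let ρ be the within-arm (multiple) correlation between the baseline covariates and the 6-month index. The documents do not give it; 0.3 and 0.5 are taken as illustrative and 0.7 as a high value.

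- Variance of the arm difference after ANCOVA ≈ (1 − ρ²) × unadjusted variance.
- Equivalent increase in sample size = 1/(1 − ρ²) − 1.
- Power, for an effect that the unadjusted two-sided 0.05 test would detect with 80% power = Φ[(1.960 + 0.842)/√(1 − ρ²) − 1.960].

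| ρ (assumed) | Variance saved | Equivalent extra subjects | Power (80% unadjusted) |
|---|---|---|---|
| 0.3 | 0.09 = 9% | 1/0.91 − 1 = 10% | Φ(2.802/0.954 − 1.960) = 84% |
| 0.5 | 0.25 = 25% | 1/0.75 − 1 = 33% | Φ(2.802/0.866 − 1.960) = 90% |
| 0.7 | 0.49 = 49% | 1/0.51 − 1 = 96% | Φ(2.802/0.714 − 1.960) = 98% |

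The expected arm difference is the same with and without the covariates, because allocation is randomized 1:1.

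**2. What post-randomization pressure does to the arm coefficient**

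Inputs from the SAP: office SBP change −9.04 (denervation) and −2.54 (control), SD 16 (Table 4); 24-hour SBP change −4.74 and −0.74, SD 12 (Table 3); drugs start at 3-month office SBP of 140 mmHg or more (9.9.10).

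Assumed, not in the documents: baseline office SBP about normal, mean 163 and SD 8, limited to 150–180; index = 1 + 0.1 per mmHg above 140 once drugs are started, plus noise with SD 1; correlation 0.6 between office and 24-hour change.

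In a simulation of 2,000,000 subjects, about 79% of denervation and 88% of control subjects reach the trigger. The arm effect on the index, adjusted for baseline pressure only, is −0.63 to −0.70, the same as unadjusted. Adding 3-month office SBP gives:

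- index set only by the 3-month reading: about 0% of the effect left;
- dose following later pressure, 80% of the variance of the 3-month change persistent: −0.107/−0.654 = 16% left;
- 60% persistent: −0.211/−0.678 = 31% left;
- 40% persistent: −0.315/−0.698 = 45% left.

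Adding 3-month 24-hour SBP instead leaves about 50% to 73%.

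The index scale is arbitrary. What carries over is the pattern: baseline pressure leaves the arm coefficient intact, and 3-month pressure shrinks it by an amount that depends on how dosing is decided after the 3-month visit.

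**The case against.** **On precision.** Randomization makes the unadjusted comparison valid, the analysis is additional with no stated power or success claim, and no document gives the correlation. All of this stands. It is why the point is a cheap improvement and not a defect. SV2 office SBP may also contribute little by itself, since entry confines it to 150 to below 180 mmHg.

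**On the SV1 record.** Protocol F.2 does not say that dose and frequency are captured, and the index needs both. Subjects off drugs for at least 4 weeks before SV1 count as drug-naive (Protocol F.3), and anti-mineralocorticoids must be stopped at least 8 weeks before SV1 (exclusion 27). An SV1 score therefore describes the regimen current at that visit, not treatment history. That is acceptable for a covariate if it is defined in those terms.

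**On the third bullet.** It sets out to find predictors, lists arm as an adjustment variable, and never says that 3-month pressure will be entered. This also stands. A reader might infer that the plan will cancel any denervation effect on medication. The documents do not support that. The first bullet still estimates the randomized effect without pressure adjustment. A coefficient of zero also requires that the whole effect pass through the pressure adjusted for, whereas Protocol F.9 leaves class, dose and later changes to the investigator and allows further visits before 6 months. What remains is that the covariates are unspecified. SAP 9.9.8 names baseline where baseline is meant; 9.9.10 does not.

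A reader might also infer that medication burden is the main outcome still comparable between arms at 6 months. SAP 9.9.8 and 9.9.9 compare blood pressure, target attainment, quality of life and medication usage at that visit too.

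**Conclusion.** The 6-month index comparison is unbiased but less precise than it need be. The saving in variance is about ρ²: 9% to 25% for an assumed correlation of 0.3 to 0.5. The true correlation is unknown, so these figures show a plausible order of size and are not a forecast. Omitting SV1 medication does not threaten validity.

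Secondarily, the pressures in the third bullet need a visit. An arm coefficient from a model containing 3-month or later pressure would be attenuated, wholly only under full mediation, and does not estimate the effect of denervation on medication. In the illustration, 3-month office SBP removes 55% to 100% of the effect and 3-month 24-hour SBP 27% to 50%, under the assumed dosing rules.

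Neither point touches the primary endpoints or the powered secondary endpoint. Label: cheap improvement.

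**What to change.** In SAP 9.9.10:

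- **First bullet.** Analyse the 6-month index by ANCOVA on arm, SV2 office SBP and SV1 index. Define the SV1 index as the score of the antihypertensive regimen current at SV1, before washout, and zero if there is none. Report the unadjusted difference with its confidence interval as a supporting result.
- **Third bullet.** Name the pressures and the visit. Use SV2 values in any model from which an arm effect is read. Label models with 3-month or later pressure exploratory, and state that their arm coefficient is not the effect of denervation on medication.

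The cost is SAP wording plus scoring the index once more from SV1 records. If dose or frequency was not captured at SV1, use the number of drug classes as the covariate instead. If the 6-month index has already been examined by arm, date the change and say so.
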